1 ABBREVIATIONS AND DEFINITIONS OF TERMS

AAR = Any Adverse Reactions

ADEXI = Adult executive functioning inventory

ANCOVA = Analysis of covariance

ASD = Autism Spectrum Disorder

BDNF = brain-derived neurotrophic factor

BFCR = Bush-Francis Catatonia Rating Scale

BOCS = Brief Obsessive Compulsive Scale

BBQ = Brunnsviken Brief Quality of Life Inventory

CGI-I = Clinical Global Impression-Improvement scale

CGI-S = Clinical Global Impression-Severity scale

CHQ-8 = Client Satisfaction Questionnaire

CNS = Central Nervous System

CRIES-8 = Children's Impact of Events Scale

DMC = Data Monitoring Committee

DSM-5 = The Diagnostic and Statistical Manual of Mental Disorders, Fifth Edition

GAF = Global Assessment of Functioning

HADS = Hospital Anxiety and Depression Scale

IVIG = intravenous immunoglobulin

M.I.N.I. = Mini International Neuropsychiatric Interview

MRI = Magnetic Resonance Imaging

MS = Multiple Sclerosis

NFL = neurofilament light chain

NGS = next generation sequencing

NIMH GOCS = National Institute of Mental Health Global Obsessive Compulsive Scale

NMDA = N-methyl-D-aspartate

NSE = eurononspecific enolase

OCD = Obsessive-Compulsive Disorder

PANDAS = Pediatric Autoimmune Neuropsychiatric Disorders Associated with Streptococcal Infection

PANS = Pediatric Acute-onset Neuropsychiatric Syndrome

PANSS-R = Positive and Negative Syndrome Scale

PGE = Patient's Global Evaluation of severity

PI = Principal investigator

PML = Progressive Multifocal Leukoencephalopathy

PNISSI = PsychoNeuroinflammatory Related Signs and Symptoms Inventory

PSP = Personal and Social Performance Scale

RAADS-R = The Ritvo Autism Asperger Diagnostic Scale-Revised

RDoC = Research Domain Criteria

SciLife Lab = Science for Life Laboratory

SLE = Systemic Lupus Erythematosus

SRIs = Serotonin Reuptake Inhibitors

SSD = Schizophrenia Spectrum Disorders

TB = Tuberculosis screen test

TNF = Tumor Necrosis Factor

UKU = UKU side effect rating scale

VGCC = Voltage-Gated Calcium Channel

WAIS = Wechsler Intelligence Scale

3 SYNOPSIS

TITLE	Rituximab - Immunotherapy for Schizophrenia spectrum disorder in adults. An open pilot study.
STUDY CENTER	Psychiatry Unit, Örebro University Hospital
AIM	To investigate whether rituximab added to treatment as usual (TAU) for 20 weeks in 12 treatment-resistant patients with schizophrenia spectrum disorder (SSD) will lead to clinically relevant overall improvement. Furthermore, the study aims to contribute to the understanding of underlying mechanisms by assessing inflammatory biomarkers in these patients.
OBJECTIVES	
Primary objective:
 
1. To investigate whether severely ill, treatment resistant, psychiatric patients with schizophrenia spectrum disorder (SSD) are significantly improved after treatment with the immunomodulatory drug rituximab (anti-CD20 antibodies) compared to baseline. 
Secondary objectives:
 
2. To examine whether baseline levels of inflammatory markers predict treatment response.3. To examine whether changes in inflammatory markers and B-cell depletion correlate with treatment response.4. To examine metabolic mediators prior and after treatment and if they correlate with treatment response.5. To examine whether there is a change in gut permeability after treatment.6. To examine whether there is a change in cognition after treatment.7. To investigate if there is a change in brain activity after treatment.8. To investigate the patients' experiences of the novel treatment with a qualitative content analysis.9. To assess safety and tolerability of rituximab during treatment for SSD

OUTCOME

Primary outcome

1. The primary outcome measure is change in symptoms measured as change in Positive and Negative Syndrome Scale (PANSS) score from baseline.

Secondary outcomes:

The secondary outcome measures are

1. Change in Personal and Social Performance Scale (PSP), measuring overall disability from baseline up to week 20
2. Change from baseline up to week 20 of illness severity (CGI-S) assessed by the clinician
3. Difference from baseline up to week 20 in inflammatory markers in blood (gene expression and proteins) in relationship to clinical response
4. Proportion of responders: Three different informants base their CGI-I evaluations on independent assessments: a) The treating clinician, b) The patient's self-assessment and c) A next of kin. If the mean value of these three is below 2.5 then the patient will be regarded as a responder (representing much or very much improved since baseline).
5. Frequency, seriousness and severity of side effects.

Other outcomes:

The other outcome measures are:

1. B-cell depletion at week 5, and B-cell subpopulations at week 20 in relation to clinical response and baseline levels of B-cells
2. Change from baseline to week 20 in

cognitive functioning

3. Change from baseline to week 20 in diagnosis specific rating scales
4. Change in brain activity in fMRI.

Long-term outcomes:

40 weeks follow – up: Primary outcome for long term is identical to that used at 20 week:

1. Change in symptoms measured as change in PANSS score from baseline

The secondary outcome measures are:

1. Difference from baseline up to week 40 in inflammatory markers in blood (gene expression and proteins) in relationship to clinical response
2. Change in Personal and Social Performance Scale, measuring overall disability from baseline up to week 40
3. Change from baseline up to week 40 of illness severity (CGI-S) assessed by the clinician
4. Life quality measured with BBQ
5. Global improvement. Three different informants base their CGI-I evaluations on independent assessments: a) The treating clinician, b) The patient's self-assessment and c) A next of kin

Other outcome measures are:

1. B-cell subpopulations at week 40 in relation to clinical response
2. Change from baseline to week 40 in cognitive functioning
3. Change from baseline to week 40 in psychiatric rating scales

POPULATION

INCLUSION CRITERIA

Twelve psychiatric patients (ages, 18-40).

- 1) patient ages 18 to 40 years
- 2) a duration of illness exceeding 2 years
- 3) correspond to "Markedly ill", "Severely ill"

or "Among the most extremely ill patients" on the Clinical Global Impression – Severity scale (CGI-S)

- 4) Global Assessment of Functioning below 50
- 5) current Diagnostic and Statistical Manual for DSM-5 diagnoses of Schizophrenia spectrum disorder
- 6) treatment resistance, i.e. failing to remit despite adequate treatments
- 7) if female and with any risk for pregnancy, willing to use contraceptives
- 8) if antipsychotic treatment is prescribed the plasma concentrations of the drug must be tested and shown to be within therapeutic interval.
- 9) subjects should be judged by the investigator to be lucid and oriented to person, place, time, and situation when giving the informed consent.
- 10) immunoglobulin levels within the normal range

EXCLUSION CRITERIA

- 1) on-going immunomodulatory treatment
- 2) pregnancy or breast-feeding
- 3) weight below 40 kg
- 4) clinically relevant on-going infection
- 5) chronic infections
- 6) positive screening test for hepatitis B, C, HIV or tuberculosis
- 7) any change of psychotropic medication within the previous 4 weeks
- 8) "much" or "very much improved" already at baseline according to CGI-I i.e. scores of 1 or 2 by the clinician
- 9) severe heart failure (NYHA grade IV) or other severe heart disease or history of cardiac

arrhythmia or myocardial infarction

- 10) unable to make an informed decision to consent to the trial
- 11) in compulsory treatment
- 12) treatment with clozapine within the last 2 months
- 13) previous treatments with immunosuppressive agents
- 14) malignancy currently or within 2 years prior to inclusion

STUDY DESIGN

Open pilot study, in addition a qualitative study using content analysis approach.

Participants will be treated initially for 20 weeks and followed for 52 weeks.

STATISTICAL ANALYSIS

Determination of Sample Size

In this pilot study population of 12 participants is presumed to be large enough to determine any effect of rituximab.

Primary objective: Effect of rituximab on schizophrenia symptoms measured with PANSS

The primary outcome (as described in section 5.2) is difference between baseline and endpoint on PANSS scale. 40% reduction in the PANSS scale.

Analyses of laboratory data related to clinical response

Laboratory data will consist of: plasma protein concentrations and leukocyte mRNA expression values for a number of cytokines and related substances (inflammatory markers); total number of B-lymphocytes and number of cells from various B-cell subsets at week 5, 12 and 20, as measured through highly sensitive flow cytometry (HSFC); plasma proteins and lipids as measured through metabolomics analysis; and blood levels of markers for gut permeability.

In order to examine whether baseline characteristics can predict treatment response, baseline values of all these measurements will

be compared in “responders” and “non-responders” after completion of the study by means of t-tests or Mann-Whitney tests, as applicable. In order to examine whether changes in inflammatory markers and other measurements correlate with clinical response, the difference between baseline values and week-20 values (Δ -values) of all relevant measurements will be compared between “responders” and “non-responders” after completion of the study by means of t-tests or Mann-Whitney tests, as applicable. In addition, for each of these measurements, a generalized linear model (ANCOVA) will be built and a PCA analysis will be performed.

Analyses of other clinical data related to clinical response

For results on the scales (Personal and Social Performance Scale, CGI-S and diagnosis specific rating scales) the week 20 scores and the Δ -values (difference between scores at week 20 and baseline) will be compared by means of t-tests or Mann-Whitney tests, as applicable. They will also be included in an analysis of covariance (ANCOVA) model, controlling for baseline measures and other possible confounders, as demographic variables.

Analyses of long-term outcomes

The results at week 40 on these variables will be analysed with essentially the same methods as those at week 20, see above.

STUDY TERMINATION

LPLV – Last Patient Last Visit

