10.2 Statistical methods and analytical plan

10.2.1 Primary objective: Improvement reflected in change in PANSS score

To investigate whether markedly ill, treatment-resistant, psychiatric patients according to our inclusion/exclusion criteria are significantly improved after treatment with the immunomodulatory drug rituximab (as addition to the patients' standard treatment).

We will analyse the clinical data on a modified intention-to-treat (ITT) definition basis, i.e. including treatment dropouts who received at least one dose of rituximab as well as completers. In addition, a completer-only analysis will be performed. *The primary outcome* is change in PANSS score, assessed by a clinician.

Secondary outcomes: CGI-I score (range 1-7). All CGI-I ratings are performed by three independent raters (the patient, his or her next of kin and a clinician). The mean value of these three values will be used as the patients' scores. If one of the values is missing, the mean will be calculated using only two values.

One secondary outcome is binary: the proportion of responders to treatment at week 20 (and similarly at week 40). Treatment response is defined as a mean value below 2.5 on the CGI-I (calculated as above), which corresponds to the scale step descriptors "much improved" or "very much improved". Non-response is defined as a mean CGI-I value of 2.5 or higher.

The continuous secondary outcome variables at the 20-week and 40-week end points (CGI-S, PSP, and diagnosis specific rating scales) will be included in analysis of covariance (ANCOVA) models, controlling for baseline measures and demographic variables.

Side-effects will be closely monitored and types, frequency, severity and seriousness will be reported.

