10.2.2 Secondary objectives: analyses of laboratory data related to clinical response

These objectives are explorative, and our hypotheses are that clinical improvement will in various ways correlate with or depend on measures of inflammation.

1. To examine whether baseline levels of inflammatory markers predict treatment response.
2. To examine whether changes in inflammatory markers between baseline and week 20, and B-cell depletion at weeks 5, 12 and 20 correlate with treatment response.
3. To examine metabolic mediators prior to and after treatment and if they correlate with treatment response.
4. To examine whether there is a change in markers for gut permeability related to treatment.
5. To examine whether there is a change in CNS activity related to reward or signs of CNS inflammation.

Laboratory data will consist of: plasma protein concentrations and leukocyte mRNA expression values for a number of cytokines and related substances (inflammatory markers); total number of B-lymphocytes and number of cells from various B-cell subsets at week 5, 12 and 20, as measured through highly sensitive flow cytometry (HSFC); plasma proteins and lipids as measured through metabolomics analysis; and blood levels of markers for gut permeability. The study of these variables in psychiatric patients is still regarded as exploratory.

All these laboratory values (except metabolomics data) will be tested for normality (Shapiro-Wilk) and homogeneity of variances (Levene's test) and, if deemed necessary, log transformation will be used to achieve normality. If normality cannot be achieved through log transformation, non-parametric test will be used for analyses.

In order to examine whether baseline characteristics can predict response from rituximab, baseline values of all these measurements (except HSFC) will be compared between the two groups "responders" and "non-responders" after completion of the study by means of t-tests or Mann-Whitney tests, as applicable. Due to the explorative nature of this study, data will be examined both corrected and un-corrected for multiple comparisons. In addition, for each of these measurements, a generalized linear model (ANCOVA) will be built, with continuous measures of clinical improvement as dependent variable and possible confounders (e.g. age, sex and BMI) as covariates.

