In order to examine whether changes in inflammatory markers and other measurements correlate with clinical response, the difference between baseline values and week-20 values (Δ -values) of all relevant measurements will be compared between the two groups "responders" and "non-responders" after completion of the study by means of t-tests or Mann-Whitney tests, as applicable. Due to the explorative nature of this study, data will be examined both corrected and un-corrected for multiple comparisons. In addition, each of these Δ -values will be introduced into a generalized linear model (ANCOVA), with continuous measures of clinical improvement as dependent variable and possible confounders (e.g. age, sex and BMI) as covariates. In addition, an exploratory principal component analysis (PCA) will be performed, in order to identify patterns of changes among the inflammatory markers that are related to clinical response.

The HSFC B-cell counts at week 5 and 12 will be used as validation of rituximab immunological impact. The clinical response will be compared with statistics as above between patients with complete ($<0.0001 \times 10^9/L$) and incomplete ($>0.0001 \times 10^9/L$) depletion of B-cells, respectively. Also B-cell subpopulations at week 20 will be correlated to clinical response.

Statistical analysis of the metabolomic data (baseline and Δ -values) will be performed similarly, however, correction for multiple comparisons by means of the Benjamini-Hochberg procedure and other methods for biostatistics and bioinformatics will be applied.

Δ -values of markers for gut permeability will be compared between pre and post treatment, in order to document whether rituximab has an effect on gut permeability.

For statistical analysis of genomic and microbiome data, appropriate methods for biostatistics and bioinformatics will be applied.

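### Marker change is related to clinical response without the marker's own baseline in the model, so part of a baseline-response association can reappear as a change-response association

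*Combined protocol and SAP*

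**What the plan says.** The synopsis (analyses of laboratory data related to clinical response) and section 10.2.2 set out two sets of marker analyses.

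- **Baseline level and response.** In section 10.2.2, "baseline values of all these measurements (except HSFC) will be compared between the two groups", that is, responders and non-responders. The synopsis plans the same comparison without the exception for the flow-cytometry B-cell data.
- **Change and response.** The plan reads "In order to examine whether changes in inflammatory markers and other measurements correlate with clinical response, the difference between baseline values and week-20 values"; these raw differences are tested in the same two groups "after completion of the study by means of t-tests or Mann-Whitney tests, as applicable". Section 10.2.2 also enters each change score in a model "with continuous measures of clinical improvement as dependent variable and possible confounders (e.g. age, sex and BMI) as covariates". The synopsis mentions a model but lists no covariates.

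For the clinical scales the plan does adjust. Section 10.2.1 analyses CGI-S, PSP and the diagnosis-specific scales by ANCOVA "controlling for baseline measures and demographic variables", and the synopsis and section 10.2.3 say the same in substance.

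The list of laboratory data in the synopsis includes "total number of B-lymphocytes and number of cells from various B-cell subsets at week 5, 12 and 20". Section 10.2.2 then gives B-cells their own analyses: week 5 and 12 counts as a check of drug effect, response by complete or incomplete depletion, and week-20 subpopulations against response. No section states a B-cell change score.

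**The concern.** Synopsis secondary objective 2 asks whether baseline marker levels predict response. Objective 3 asks whether marker changes go with response. A reader will take positive answers to both as two findings. They are not separate, because the change score is partly the baseline with its sign reversed. If responders start higher on a marker, regression to the mean alone makes them appear to fall more, which is the pattern the inflammatory hypothesis in section 4.1 predicts. Correcting for multiple comparisons does not remove this, because the problem is confounding by baseline and not the number of tests.

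At stake is the reading of the mechanism analysis at week 20, and at week 40, where section 10.2.4 carries over essentially the same methods.

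**Working it through.** **Inputs from the documents.** 12 patients in a single arm (synopsis). The change score is the baseline to week-20 difference. The tests are t-test or Mann-Whitney, plus a model with age, sex and BMI as example covariates (section 10.2.2). No power calculation or significance level is given for these analyses. The one precision figure, 0.64 CGI-I points in section 10.1, reproduces as 2.201 × 1/√12 = 0.635 but does not concern the markers.

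**Assumptions.** Two-sided 5% level; r = correlation between baseline and week 20; equal variances at the two visits; change = week 20 minus baseline. The plan does not fix the direction of the laboratory difference; reversing it flips signs, not sizes.

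**Step 1: overlap of change and baseline.** corr(change, baseline) = -√((1-r)/2).
- r = 0.3: -√0.35 = -0.59
- r = 0.5: -√0.25 = -0.50
- r = 0.7: -√0.15 = -0.39

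**Step 2: size of the carry-over.** A baseline difference of d SD between responders and non-responders gives an expected change difference of -(1-r)d. At d = 1 this is -0.5 SD for r = 0.5 and -0.2 SD for r = 0.8, so the carry-over is partial.

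**Step 3: effect on the tests, n = 12.** Simulation of the change-improvement correlation, 40,000 runs, with week 20 adding nothing once baseline is known:

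| Relation of baseline to improvement | r = 0.3 | r = 0.5 | r = 0.7 |
|---|---|---|---|
| Correlation 0.6, change unadjusted | 21% | 16% | 11% |
| Correlation 0.6, baseline added | 5% | 5% | 5% |
| None, change unadjusted | 5% | 5% | 5% |

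The plan's own test forms give the same picture:

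| Unadjusted analysis of change | r = 0 | r = 0.5 | r = 0.8 |
|---|---|---|---|
| t-test, 4 responders and 8 non-responders, d = 1 | 17.8% | 11.5% | 7.5% |
| Model with age, sex, BMI; baseline correlated 0.5 with improvement | 14.6% | 9.6% | 6.9% |
| Same model; baseline correlated 0.7 with improvement | 27.5% | 15.6% | 9.1% |

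All return to about 5% with the marker's baseline added.

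**Step 4: cost of adjusting.** The planned model has an intercept, change, age, sex and BMI, leaving 12 - 5 = 7 residual degrees of freedom; with baseline, 6. If improvement depends on change itself (correlation 0.6), adding baseline lowers power from about 58% to 39%, 44% and 48% at r = 0.3, 0.5 and 0.7 (no other covariates in the model).

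**Step 5: B-cells, if a change score were used.** Assume a median baseline of 0.2 × 10⁹/L. With every week-20 count below the plan's 0.0001 × 10⁹/L threshold, corr(change, baseline) = -1.00. If patients recover 0-10%, 0-50% or 0-100% of baseline by week 20, the median correlation is -0.997, -0.90 or -0.55.

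**The case against.** **The covariate list is open.** Section 10.2.2 gives "possible confounders (e.g. age, sex and BMI) as covariates", so the marker's baseline could still be added. This stands: it is an omission, not a stated exclusion. It does not help the t-tests and Mann-Whitney tests, which take no covariate.

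**The plan asks only whether change correlates with response.** In the scenario of step 3, change does correlate with improvement: 0.6 × (-0.59, -0.50, -0.39) = -0.35, -0.30, -0.23. On that marginal question the 21%, 16% and 11% are not false positives, and with no baseline relation the test holds its 5% level. This also stands. The fault lies in reading the result as information beyond baseline level, so the unadjusted comparison can stay, with the adjusted one beside it.

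**Adjustment can cost power.** Correct, as step 4 shows. A reader might infer that adding baseline generally gains power. That depends on which relation is true, so no such gain is claimed.

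**B-cells.** A reader might infer that the plan tests a B-cell change score that is simply the baseline count with its sign reversed. The documents do not support this. The named B-cell analyses use depletion status and week-20 values, and the B-cell outcome (synopsis and section 5.2) also refers to baseline B-cell levels. No expected week-20 count is given, there is one infusion, and incomplete depletion is allowed for. What remains is an ambiguity: B-cell counts are in the laboratory list, the flow-cytometry exception covers only the baseline comparison, and the change analysis applies to all measurements deemed relevant.

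**Exploratory status.** Section 10.2.2 labels these objectives explorative, and results are shown with and without multiplicity correction. That limits the consequence but does not separate change from baseline.

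**Conclusion.** The concern holds in limited form. As written, the marker change analyses cannot show whether change relates to response beyond baseline level, and a positive answer to objective 3 may partly repeat objective 2. The size depends on two quantities the documents do not give: the marker's stability and the strength of its baseline relation to improvement. For r of 0.3 to 0.7 and a baseline correlation of 0.6, the unadjusted test is significant in 21% to 11% of trials against 5% adjusted. For a stable marker (r = 0.8) and a 1 SD baseline difference, it is about 7-8%.

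The documents do not support reading this as a general inflation of error, since the rate is 5% when baseline is unrelated to improvement. Nor does it reach the primary PANSS outcome. It is a cheap improvement to an exploratory mechanism analysis.

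**What to change.** 1. In the change-score models of section 10.2.2, and in the matching synopsis text, name the marker's own baseline as a covariate. Regressing improvement on the week-20 value plus baseline gives the same test.
2. Report this model next to the unadjusted comparison, and claim that change relates to response independently of baseline level only from the adjusted model. Apply the same rule at week 40.
3. State that B-cell counts and subsets are not among the measurements analysed as change scores, and are analysed by depletion status and post-treatment values as section 10.2.2 already sets out. If counts are still depleted at week 20, change would nearly duplicate baseline, and adding baseline could not separate them.

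The cost is a few sentences, a covariate already collected, and one residual degree of freedom (7 to 6). The adjusted model has lower power where improvement depends on change itself (about 58% to 39-48%), which is a reason to show both results.
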